The study consists of a Core Study followed by an open-label Extension Phase. The Core Study is a 24-month treatment with 3-month follow up, multicenter, double-blind, placebo-controlled, parallel-group study in EAD including mild cognitive impairment (MCI) due to AD/Prodromal AD and the early stages of mild AD. In addition, the MCI due to AD population will also be consistent with the research criterion for “Prodromal AD” in that episodic memory will be impaired on a list-learning task (International Shopping List Task [ISLT]). The Extension Phase is available for subjects who complete the Core Study and provides subjects with open-label treatment with elenbecestat for 24 months, or until commercial availability of elenbecestat or a lack of positive benefit-risk is determined, whichever comes first. (revised per Amendment 05)

Study E2609-G000-301 and Study E2609-G000-302 will be combined with a total of approximately 1900 randomized subjects; at least 850 subjects will be randomized in each study. (revised per Amendment 05)

In this Core Study, subjects will be randomized in a double-blind manner, to receive either placebo or elenbecestat 50 mg per day (approximately 1:1 randomization ratio) for 24 months. Randomization will be stratified according to region (7 levels), clinical dementia staging (with no more than approximately 25% of the randomized subjects diagnosed with the early stages of mild dementia due to AD), and concurrent AD medication use. The 7 levels of region are:

1. North America
2. Western Europe (including Oceania region and South Africa)
3. Eastern Europe
4. Japan
5. China
6. Other Asian countries

7. South America

(revised per Amendment 05)

The study is designed to have more frequent visits focused on safety assessments during the first 3 months of treatment.

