The *ApoE* genotype for all subjects and NAT2 genotype in a subset of subjects will be determined from blood specimens using validated assays. (revised per Amendment 03)

Plasma concentrations of elenbecestat that may extend to the key metabolites M1, M2, and M5 will be measured by a validated assay using liquid chromatography method using tandem mass spectrometry.

A β (1-x) and other relevant biomarkers will be measured in the blood samples collected at times that match the PK draws and during the Follow-up Period. (revised per Amendment 01)

Statistical Methods

All statistical analyses will be performed by the sponsor or designee after the study is completed and the database is locked and released for unblinding. All statistical analyses will be performed based on the pooled data from 2 studies (E2609-G000-301 and E2609-G000-302). The analyses will also be performed within each study to confirm the trend of the efficacy and biomarker endpoints unless specified. (revised per Amendment 05)

Core Study

Study Endpoints

Primary Endpoint

- Change from baseline in the CDR-SB at 24 months in the combined studies (revised per Amendment 05)

Key Secondary Endpoints (revised per Amendment 05)

- Change from baseline in ADCOMS at 24 months in the combined studies
- Change from baseline in amyloid PET SUVR at 24 months for brain amyloid levels in the combined studies
- Change from baseline in amyloid PET SUVR at 24 months for brain amyloid levels in the individual studies

Other Secondary Endpoints (revised per Amendment 05)

- Change from baseline in the CDR-SB at 24 months for subjects enriched by baseline PET SUVR, eg, between 1.2 and 1.6, in the combined studies
- Change from baseline in the ADCOMS at 24 months for subjects enriched by baseline PET SUVR, eg, between 1.2 and 1.6, in the combined studies
- The rate of change over time (mean slope) based on CDR-SB score over 24 months in the combined studies
- Time to worsening of CDR scores by 24 months (eg, the worsening of global CDR score is defined as an increase from baseline by at least 0.5 points on the global CDR scale on 2 consecutive scheduled visits at which global CDR is undertaken) in the combined studies
- Time to conversion to dementia by 24 months for subjects who were not clinically staged as dementia at Baseline based on clinical diagnosis in the combined studies

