- The PD Analysis Set is the group of subjects who have sufficient PD data to derive at least 1 PD parameter.

Efficacy Analyses

The FAS will be used as the primary population for all efficacy analyses, while the PPS will be used as the supportive population.

Analyses for Primary Efficacy Endpoints

The primary analysis will be based on an intent to treat philosophy without regard to adherence to treatment. The primary analysis of the change from baseline in CDR-SB at 24 months will be performed to compare elenbecestat 50 mg per day versus placebo using a linear mixed effects model for repeated measures (MMRM) on the FAS. The MMRM model will include fixed effects of treatment group, visit, treatment group by visit interaction, baseline CDR-SB, baseline CDR-SB by visit interaction, and randomization stratification variables (ie, region [7 levels], clinical dementia [yes, no], and concurrent AD medication use at randomization (Visit 2) [yes, no]). *ApoE4* status may be included in the model if appropriate. (revised per Amendment 05) An unstructured covariance matrix will be employed to model the covariance of within subject effect; if MMRM fails to converge then a covariance structure with fewer parameters from the following list will be employed according to the prespecified order in the list until the MMRM converges. The list of covariance structure will include Heterogeneous Toeplitz, Toeplitz, Heterogeneous Compound Symmetry, and Compound Symmetry. This primary analysis will include all observed post baseline data of the change from

baseline in CDR-SB without imputation of missing values. The treatment effect for elenbecestat versus placebo will be compared at 24 months based on MMRM model. The LS means and difference in LS means between elenbecestat treatment group and placebo, and corresponding 95% confidence interval (CI) will be presented.

The null hypothesis is that there is no difference in the mean change from baseline in CDR-SB at 24 months between elenbecestat 50 mg per day and placebo. The corresponding alternative hypothesis is that there is a difference in the mean change from baseline in CDR-SB at 24 months between elenbecestat 50 mg per day and placebo.

The primary analysis will be repeated to minimize the impact of change in concomitant AD medications where efficacy data after initiation of new AD medications and increase of current AD medications will be censored.

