The following sensitivity analysis will be conducted to evaluate the impact of missing data: the primary endpoint will be analyzed using analysis of covariance model (ANCOVA) after multiple imputation. The ANCOVA model will include baseline CDR-SB as a covariate, with treatment group, and randomization stratification variables as factors. *ApoE4* status may be included in the model if appropriate. Additional sensitivity analyses will be performed to assess the robustness of the missing at randomization assumption in the primary MMRM model.

Subgroup analysis (eg, stratification factors and *ApoE4* status) and additional sensitivity analysis for the primary endpoint will be performed as appropriate. (revised per Amendment 05)

Analyses for Key Secondary Efficacy Endpoints (revised per Amendment 05)

The key secondary analyses will be performed only if the primary analysis is significant. The treatment effect for elenbecestat 50 mg/day versus placebo, for each key secondary efficacy endpoint, will be tested using a sequential testing procedure at a significance level of 2-sided alpha = 0.05, ie., any test will start only if the test with higher hierarchical order is significant.

The change from baseline in ADCOMS at 24 months will be analyzed using the same MMRM model as the primary efficacy analysis to compare elenbecestat 50 mg per day versus placebo on the FAS, using baseline ADCOMS in the model.

The change from baseline in amyloid PET SUVR at 24 months will be analyzed using the same MMRM model as the primary efficacy analysis to compare elenbecestat 50 mg per day versus placebo on the FAS, using baseline amyloid PET SUVR in the model. The same analysis will be performed within study as key secondary efficacy endpoint analyses.

Analyses for Other Secondary Endpoints (revised per Amendment 05)

The change from baseline in CDR-SB and ADCOMS at 24 months will be analyzed using the same MMRM model as the primary analysis for subjects enriched by baseline PET SUVR between eg, 1.2 and 1.6 on the FAS.

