The rate of change over time (mean slope) based on change from baseline in the CDR-SB will be analyzed using linear mixed effects (LME) models for multivariate normal data derived from a random coefficient model (slope analysis), where the mean slope in each group depends on a continuous assessment time. The LME model will include treatment group, baseline CDR-SB, randomization stratification variables, assessment time, baseline CDR-SB-by-assessment time, and treatment group-by-assessment time. *ApoE4* status may be included in the model if appropriate.

Time to worsening of CDR scores by 24 months will be analyzed on the FAS using Cox regression model for treatment effect adjusting for randomization stratification factors. *ApoE4* status may be included in the model if appropriate. (revised per Amendment 05) Time to worsening of a CDR score

is defined as time from randomization to worsening of the CDR score (ie, the first worsening in 2 consecutive scheduled visits). For subjects whose CDR scores have not worsened by the end of the Treatment Period of the Core Study, the time to worsening of the CDR score will be censored at the date of last CDR assessment for these subjects.

Time to conversion to dementia for subjects who were not clinically staged as dementia at Baseline based on clinical diagnosis will be analyzed on the FAS using Cox regression model for treatment effect adjusting for randomization stratification factors. *ApoE4* status may be included in the model if appropriate. (revised per Amendment 05) Proportion of subjects with dementia diagnosis at 24 months will be estimated using Kaplan–Meier method based on time to conversion to dementia based on clinical diagnosis. Time to conversion to dementia for subjects who were not clinically staged as having dementia at Baseline based on clinical diagnosis is defined as time from randomization to conversion to dementia based on clinical diagnosis. For subjects without clinical dementia by the end of study, the time to conversion to dementia based on clinical diagnosis will be censored at the date of last dementia diagnosis.

The other continuous secondary efficacy endpoints as defined above will be analyzed using the same MMRM model as the primary efficacy analysis to compare elenbecestat 50 mg per day versus placebo on the FAS, using baseline value corresponding to the response variable in the model.

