The sample size for this study is estimated for comparison of elenbecestat versus placebo with respect to a pooled analysis of studies E2609-G000-301 and E2609-G000-302 for the change from baseline in CDR-SB at 24 months. Based on the available data from the placebo group in Study BAN2401-G000-201 (a recently completed study with a comparable subject population), the mean and the standard deviation of the change from baseline in CDR-SB at 24 months in the placebo group are assumed to be 1.46 and 2.05, respectively, instead of 1.75 and 2.05, which are originally assumed by the available data from ADNI (of amyloid positive, MMSE equal or greater than 24, late MCI [global CDR=0.5, CDR memory box \geq 0.5]) is selected to estimate the mean and standard deviation of the change from baseline in CDR-SB at 24 months in the placebo group, which are 1.5 and 2.05, respectively. Therefore, assuming a 25% reduction in the mean change from baseline CDR-SB at 24 months for elenbecestat compared to placebo with common standard deviation of 2.05 and 30% dropout rate, a total sample size of 1900 subjects, 950 subjects in each treatment group, will be required to detect the treatment difference between elenbecestat and placebo using a 2-sample t test with 90% power at a significance level of 2 sided alpha =0.05.

The pooled data from 2 studies (E2609-G000-301 and E2609-G000-302) will comprise the total sample size of approximately 1900 subjects. At least 850 subjects will be randomized in each study. (revised per Amendment 05)

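### The models for the pooled analysis of Studies 301 and 302 contain no study term, although subjects are randomised within each study: a small gap that costs almost nothing to close

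*Protocol*

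**What the plan says.** The Version 7.0 synopsis, under Statistical Methods, puts the analyses on combined data: "All statistical analyses will be performed based on the pooled data from 2 studies (E2609-G000-301 and E2609-G000-302". The two trials stay separate in allocation. The Sample Size Rationale plans about 1900 subjects in total and adds "At least 850 subjects will be randomized in each study".

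Under Analyses for Primary Efficacy Endpoints the model terms are listed: "The MMRM model will include fixed effects of treatment group, visit, treatment group by visit interaction, baseline CDR-SB, baseline CDR-SB by visit interaction", together with "randomization stratification variables (ie, region [7 levels], clinical dementia [yes, no], and concurrent AD medication use at randomization (Visit 2) [yes, no". One further term is optional: ApoE4 "status may be included in the model if appropriate". ADCOMS and amyloid PET SUVR use the same MMRM.

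For the sensitivity analysis after multiple imputation: "The ANCOVA model will include baseline CDR-SB as a covariate, with treatment group, and randomization stratification variables as factors". The slope model lists treatment, baseline, the stratification variables, time and two interactions with time. Each time-to-event endpoint "will be analyzed on the FAS using Cox regression model for treatment effect adjusting for randomization stratification factors". None of these lists names study.

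Analyses within each study are also planned, but to confirm the trend. The exception is amyloid PET SUVR, where the within-study analysis is itself a key secondary.

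**The concern.** When two trials are pooled and each has its own randomisation, study is in effect a stratification factor of the combined allocation. The usual rule is to analyse by the factors within which subjects were randomised, and the synopsis follows it for region, dementia stage and AD medication but not for study.

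Three things could follow. First, any difference in mean decline between the studies stays in the residual variance. Second, the treatment contrast can pick up between-study information if the balance of arms at month 24 is not the same in both studies. Third, the MMRM uses observed data without imputation, and the plan assumes 30% dropout. If study predicts both dropout and decline, leaving it out weakens the missing-at-random assumption of the MMRM and of the analysis after imputation.

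**Working it through.** **Inputs.** From the Sample Size Rationale (Version 7.0): placebo change 1.46, SD 2.05, 25% reduction, 30% dropout, two-sided alpha 0.05, 90% power, 950 per arm. From Study Design: about 1:1 allocation. Assumed, because the documents give no figure: the gap g between the studies in mean 24-month change, and any difference in study mix between the arms. The studies are taken as equal in size.

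**1. The plan's own figure.** Effect = 0.25 × 1.46 = 0.365. A two-sample comparison needs 663 completers per arm. 663 / 0.70 gives 948 per arm, 1896 in total, which agrees with 1900. (The same paragraph also states a placebo mean of 1.5; that gives 899 per arm, 1798 in total, and does not reproduce 1900.) The calculation treats the pooled data as one trial. Completers at the planned size: 950 × 0.70 = 665 per arm. Adding study leaves this calculation unchanged if 2.05 is read as the within-study SD.

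**2. Power and type I error without study.** With exact 1:1 allocation in both studies, the true standard error is 2.05 × √(2/665) = 0.1124. A model without study estimates its residual SD as s = √(2.05² + g²/4), which is too large. With r = s / 2.05:

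- type I error = 2 × [1 − Φ(1.96 r)]
- power = Φ(0.365 / 0.1124 − 1.96 r)

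| Assumed gap g | s | r | Type I error | Power |
|---|---|---|---|---|
| 0 (or study in the model) | 2.0500 | 1.000 | 0.0500 | 0.9009 |
| 0.25 | 2.0538 | 1.002 | 0.0496 | 0.9003 |
| 0.5 | 2.0652 | 1.007 | 0.0483 | 0.8983 |
| 1.0 | 2.1101 | 1.029 | 0.0437 | 0.8905 |

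The loss is at most about 1 percentage point of power, and the test moves to the conservative side.

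**3. Bias.** Bias = g × (share of the active arm from one study − share of the placebo arm from that study), at month 24.

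- Same arm balance in both studies: difference 0, bias 0 for any g.
- Active share 52% in one study and 48% in the other: 0.52 − 0.48 = 0.04. At g = 0.25 the bias is 0.010 points (2.7% of 0.365); at g = 0.5 it is 0.020 (5.5%).
- Difference of 0.05 and g = 0.6: 0.030 points (8.2%).

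A difference of 0.05 is not easily reached. For example, active-arm retention would have to be 77% in one study and 63% in the other, with placebo at 70% in both: 77/140 = 0.55 against 70/140 = 0.50. A higher dropout in one arm that is the same in both studies leaves the mix unchanged.

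**The case against.** The case for leaving the model alone has some force. The revision history calls the trials identical, and region, dementia stage, AD medication and baseline CDR-SB are already adjusted for. Only the gap that remains after this adjustment matters, and 0.6 points would be 41% of the assumed placebo change (0.6 / 1.46). The bias product in the working is a completer-mean formula. The MMRM also uses earlier visits of subjects who drop out, so the product is nearer an upper bound. All of this stands and keeps the point small.

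The within-study analyses would show a marked difference between the trials, but they do not replace the term. At 850 per study with 30% dropout, each has about 58% power (297.5 completers per arm), and the confirmatory claim rests on the pooled model.

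The full Version 7.0 Section 9.7.1.6 and the SAP are not available and may contain study. That limits certainty. It does not alter the fact that the synopsis states a definite list that leaves study out.

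A reader might infer three stronger things, and the documents support none of them:

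- That the model was simply left over from the single-study design. An older Section 9.7.1.6.1 in the same file has six regions, no baseline-by-visit term and no ApoE4 option. The Version 7.0 list has seven regions and both terms, and is marked as revised under Amendment 05, which also introduced pooling. The list was rewritten without study being added.
- That the type I error is inflated. Under 1:1 allocation it falls slightly.
- That the optional ApoE4 term is part of this problem. That wording is loose, but it is a separate matter and adds nothing to the weight of this one.

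**Conclusion.** The point holds as a specification gap of minor to moderate severity. No pooled model stated in the Version 7.0 synopsis includes study, although study is a factor within which subjects are randomised. For assumed gaps of 0.25 to 1.0 CDR-SB points the cost is 0 to 1 percentage point of power, with a slightly conservative test. Bias of about 0.01 to 0.03 points is possible for gaps up to 0.6, but only if the balance of arms at month 24 differs between the studies; with equal balance it is zero. These sizes rest on assumed gaps and imbalances, equal study sizes and an SD of 2.05 within study. They do not suggest that the planned test would be invalid or materially underpowered. The reason to change it is that the confirmatory model should match the pooled design, and doing so is practically free.

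**What to change.** Add study (301 or 302) as a fixed effect in the pooled MMRM for CDR-SB, ADCOMS and amyloid PET SUVR, in the imputation model, in the ANCOVA and in the slope model. In the pooled Cox models include study as a covariate or as a stratum; either is acceptable. The within-study analyses need no change. A study-by-visit term is a matter of preference, since none of the other stratification factors has one.

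Make the change before unblinding, in the synopsis, Section 9.7.1.6 and the SAP together. If the latter two already contain study, align the synopsis with them. The cost is wording and one degree of freedom per model for the main effect; sample size, data collection and planned power are not affected.

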The Randomization Phase consists of a Treatment Period and a Follow-up Period. The Treatment Period will last 24 months. Subjects will be randomized at Visit 2 (Day 1) to receive elenbecestat 50 mg per day or placebo administered orally, once daily (QD) in the morning with or without food. During Visit 2, the subject will complete additional baseline assessments before receiving the first dose of study drug: MMSE, CDR, ADAS-cog14, FAQ, and NPI-10. Inclusion and exclusion criteria will be reviewed again together with concomitant medications and assessment of adverse events (AEs). A single 12-lead ECG will be conducted. The C-SSRS will also be administered. A baseline routine physical examination with dermatologic review, vital signs measurements, clinical laboratory testing, urinalysis using urine dipstick, and a urine pregnancy test (females of child-bearing potential only), will be performed. Additional blood samples will be taken and stored.

During the Randomization Phase all subjects will undergo assessments of cognition, daily function, quality of life, safety, PK, PD, MRI, and vMRI (including sequences for fMRI), while those subjects who consent to participate in the amyloid PET, tau PET, and/or CSF longitudinal substudies will undergo additional assessments as indicated in the protocol. (revised per Amendments 01 and 04)

The CDR will be conducted every 3 months during the Core Study; other cognitive assessment instruments will be administered every 6 months. Every 3 months, the investigator is required to confirm the clinical staging of disease (ie, dementia or nondementia). This staging decision will be verified via a central review process and adjudicated if necessary (adjudication will only occur when there is a discrepancy between the clinical disease staging made by the site compared to that determined by the central review process; moreover, where adjudication is required, it will be undertaken by an independent assessor(s)).

The health-related quality of life measures will be conducted every 6 months during the Core Study along with the NPI-10.

MRI scans (including vMRI and fMRI) will be performed at 12 and 24 months during the Core Study or at the Early Discontinuation (ED)/Follow-up Visit. If subjects have non-MRI compatible devices fitted during treatment, then a computed tomography scan may be utilized to assess safety, if deemed appropriate by the investigator. (revised per Amendment 05)

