 - b. CDR global score of 0.5
 - c. CDR Memory Box score of 0.5 or greater
2. A history of subjective memory decline with gradual onset and slow progression over the last 1 year before Screening; this MUST be corroborated by a study partner
3. Cognitive impairment of at least 1 SD from age-adjusted norms in total recall or delayed recall on the ISLT.
4. Positive biomarker for brain amyloid pathology as indicated by at least 1 of the following:
 - a. PET assessment of amyloid imaging agent uptake into brain. Note: amyloid PET screens will be performed according to local regulatory guidelines and thus may be restricted for those subjects who are not suitable for lumbar puncture (LP) to obtain CSF for testing of eligibility.
 - b. CSF AD assessment(eg, tau:Aβ(1-42) ratio) (revised per Amendment 03)

NOTE: Subjects may undergo both the amyloid PET and CSF assessments, but need a positive amyloid result in only 1 of the 2 procedures to confirm eligibility. Subjects who consent to amyloid PET or CSF for eligibility purposes are not required to participate in the amyloid PET or CSF longitudinal substudies. Use of a historical amyloid positive PET (conducted within 12 months before the planned date of randomization) is acceptable for determination of eligibility but will not suffice for the baseline assessment if the subject wishes to consent to the amyloid PET longitudinal substudy. The historical imaging data must be made available to the sponsor. Historical CSF samples, if collected, processed, and stored under appropriate conditions and approved by the sponsor, may be analyzed to determine CSF amyloid positivity. (revised per Amendments 03 and 05).
5. Male or female subjects between 50 and 85 years of age, inclusive at the time of consent
6. If receiving an acetylcholinesterase inhibitor (AChEI) or memantine or both for AD, must be on a

stable dose for at least 12 weeks before Randomization. Treatment-naïve subjects with AD can be entered into the study.

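### The primary MMRM does not adjust for baseline ADAS-cog14 or age, though both are known before the first dose: a near-free efficiency missed, not an error

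*Protocol*

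**What the plan says.** The Version 7.0 synopsis, under the analyses for the primary endpoint, lists the model terms in full. The list opens: "The MMRM model will include fixed effects of treatment group, visit, treatment group by visit interaction, baseline CDR-SB". The part after treatment and visit reads, to its end, "treatment group by visit interaction, baseline CDR-SB, baseline CDR-SB by visit interaction, and randomization stratification variables". The stratification factors are "region [7 levels], clinical dementia [yes, no], and concurrent AD medication use at randomization (Visit 2) [yes, no"]. One further covariate is left open: ApoE4 "status may be included in the model if appropriate". The model uses observed post-baseline data without imputation. The sensitivity analysis, an ANCOVA after multiple imputation, adjusts for baseline CDR-SB and the stratification factors, again with ApoE4 optional.

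Two other baseline variables are at hand. At Visit 2 the subject completes "additional baseline assessments before receiving the first dose of study drug: MMSE, CDR, ADAS-cog14, FAQ, and NPI-10". Age is fixed by the eligibility criteria and spans 35 years: "Male or female subjects between 50 and 85 years of age, inclusive at the time of consent". Neither baseline ADAS-cog14 nor age appears in the primary model or in the imputation-based ANCOVA.

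The sample size rationale uses a two-sample t test with an SD of 2.05 and no covariate adjustment.

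**The concern.** Pre-dose covariates that are named in advance do not bias a randomised comparison. Where they predict the outcome, they reduce its residual variance.

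There is a plausible case that baseline ADAS-cog14 carries information on severity that baseline CDR-SB lacks. Entry requires a global CDR of 0.5, which limits the spread of CDR-SB. The synopsis describes ADCOMS as built from CDR, MMSE and ADAS-cog14 items in order to be sensitive to progression. MMSE is a less attractive candidate because entry confines it to 24 to 30.

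Two things are at stake. The first is some precision in the primary test of a programme that now has to pool two studies to reach 1900 subjects. The second is the missing-data assumption. With 30% dropout planned for, the MMRM relies on data being missing at random given the terms in the model. If dropout also depends on baseline cognition or age, including them makes that assumption easier to defend.

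**Working it through.** **Inputs from the Version 7.0 sample size rationale.** Placebo mean and SD in "the placebo group are assumed to be 1.46 and 2.05, respectively, instead of 1.75 and 2.05"; effect from "assuming a 25% reduction in the mean change from baseline CDR-SB at 24 months for elenbecestat compared to placebo"; 30% dropout; two-sided alpha 0.05; 90% power; 1900 subjects in total, 950 per arm.

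**Reproducing the plan's figure.**
- Difference = 0.25 × 1.46 = 0.365.
- n per arm = 2 × (1.960 + 1.282)² × 2.05² / 0.365² ≈ 663.
- Allowing for dropout: 663 / 0.70 ≈ 948 per arm, or 1896 in total. The noncentral t version gives 664, 949 and 1898. Both agree with 1900.
- The same paragraph also prints a placebo mean of 1.5, which gives 1798. The planning value behind 1900 is therefore 1.46.

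**Power as planned.** Completers per arm = 950 × 0.70 = 665. SE = 2.05 × √(2/665) = 0.1124. The ratio 0.365 / 0.1124 = 3.25, and the t-test power is 90.0%.

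**Effect of adjustment.** Let R² be the share of remaining variance that baseline ADAS-cog14 and age explain beyond the planned terms. The protocol gives no value, so a range is assumed. Residual SD = SD × √(1 − R²).

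Applied to the raw SD of 2.05, with 665 completers per arm:

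| Assumed R² | Residual SD | SE | Power (t test) |
|---|---|---|---|
| 0% | 2.050 | 0.1124 | 90.0% |
| 1% | 2.040 | 0.1119 | 90.3% |
| 3% | 2.019 | 0.1107 | 90.9% |
| 5% | 1.998 | 0.1096 | 91.4% |
| 10% | 1.945 | 0.1067 | 92.8% |

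This table treats the raw SD as if the planned covariates explained nothing. A fairer start is the residual SD after those terms. If they explain an assumed 10%, that SD is 2.05 × √0.90 = 1.945 and power is already 92.8%. Then:
- a further 3%: SD 1.945 × √0.97 = 1.915, power 93.5%, a gain of 0.7 points;
- a further 5%: SD 1.945 × √0.95 = 1.896, power 93.9%, a gain of just under 1.2 points.

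Both calculations count completers only. The MMRM also uses data from subjects who leave early, so they approximate the planned analysis.

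**The case against.** The strongest reply is that nothing in the plan is wrong. The MMRM is valid and the 90% power takes no credit for any covariate. That stands, and it is why this is a missed efficiency and not a defect.

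A reader might infer that the model adjusts for baseline CDR-SB and strata alone. It does not: it also lets the baseline CDR-SB effect vary by visit, leaves room for ApoE4, and includes clinical dementia (yes or no), which is itself a severity term.

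A reader might also infer that baseline CDR-SB separates fast from slow decliners poorly, or that ADAS-cog14 and age are known to do better. No part of the protocol shows this. The ADCOMS rationale concerns responsiveness over time, which is different from a baseline score predicting later CDR-SB change. Nothing links age to CDR-SB change either. A true incremental R² near zero cannot be excluded.

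On missing data, dependence of dropout on cognition or age beyond the planned terms is likewise unsupported. The plan already offers some protection: CDR every 3 months, return visits at 12 and 24 months after stopping drug, multiple imputation, and further sensitivity analyses of the missing-at-random assumption.

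What survives is narrower. The covariate list is a choice the protocol itself makes, the data are already collected, and prespecified adjustment has little downside in a trial of this size.

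**Conclusion.** The point holds as a low-cost improvement. The Version 7.0 primary model omits baseline ADAS-cog14 and age although both are known before the first dose, and adding them can be expected to keep or improve precision.

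The size is modest and uncertain. It is 0 to about 2.7 power points for an assumed incremental R² of 0% to 10% on the raw SD, and about 0.7 to 1.2 points for a further 3% to 5% if the planned terms already explain an assumed 10%. It would be wrong to conclude that the trial is underpowered or its primary test compromised: the stated sample size reproduces, and the analysis is sound as written.

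This rests on the synopsis. The Version 7.0 body section on the primary analysis (9.7.1.6.1) is not among the parts available.

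**What to change.** Before unblinding, name baseline ADAS-cog14, with its interaction with visit, and age as fixed covariates in the primary MMRM. Use the same covariates in the multiple-imputation model and in the ANCOVA that follows it. Decide at the same time whether ApoE4 is in or out, so that the covariate list is closed.

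The ADCOMS model need not change: it already adjusts for baseline ADCOMS, which contains ADAS-cog14 items.

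The cost is wording in the protocol or SAP, a few degrees of freedom against about 1330 expected completers (2 × 665), and a simple prespecified rule for the rare missing baseline score. No new visit or assessment is needed.
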